1. SPIED Study Emergency Department Data Form [Appendix 4]
 - a. Emergency Department staff may choose to use this form in place of Medical Surveys should they prefer, or if there are logistical challenges encountered with Medical Surveys
2. Limb Observation Chart: [Appendix 6]
 - a. It is standard practice on the surgical ward for nursing staff to complete limb observations every 1-2 hours on patients with #NOF and record these on a limb observation chart.
 - b. This chart has been modified for the SPIED study to also record pain scores
 - c. Also includes pain score calculators for the VAS and PAINAD
3. Subjective Observed Patient Comfort During Nursing Cares [Appendix 7]

Primary outcome = reduction of pain score

VAS pain scores will be recorded at rest and on movement. Movement is defined as attempted hip flexion to 15 degrees. PAINAD scores will be single measure based on nursing observation.

This score will be documented at the following times:

- Prior to placement of nerve block in the emergency department
- 15, 30, 60 minutes post placement of block
- With routine limb observations on the surgical inpatient ward, approximately hourly

Data will be collected for 12 hours post nerve block (or the next documented score after 12 hours) or until the patient is moved to the operating room, whichever is sooner.

Sample size and statistical power

The rationale for sample size calculations:

- A reduction in visual analogue pain score of 13 mm (1.3/10) was established as being clinically significant by Todd et al in 1996 [26].
- A clinically significant difference between two treatments that reduce pain scores by 1.3/10 has not been well defined
- Cooper et al used 1.5/10 difference in pain scores as a definition of clinically significant difference between blocks [27].
- Newman et al found a standard deviation in pain score reduction of 2.4 in patients receiving regional analgesia for #NOF in 2013 [28]. This figure was used by Cooper et al for their power calculation in 2018.
- Cooper et al found standard deviations of 2.2 and 2.4 respectively for the FNB and FICB [27].
- A retrospective study of patients that received regional anaesthesia for # NOF at LBH in the first 4 months of 2019 was performed by co-investigators of this study. This data included 40 patients that received regional anaesthesia in ED, 6 of whom received a PENG block. Pain score documentation was not sufficiently reliable to inform power calculations for this observational study.

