Minimum Sample Size Calculation: Application of Student's t-Test.

Calculation assisted by using the Simple Sample Size Calculator (Android application). [Appendix 2]

- One-sided test to assess for non-inferiority
- Two sample
- Error 0.05
- Sample allocation ratio of 1:2
- Standard Deviation = 2.4
- $\mu_0 = 4$, $\mu_1 = 2.5$ (difference in pain score reduction of 1.5)
- Target (Actual) Power = 0.8000
- **Sample size = 74 (25+49)**

Duration of Data Collection

At our institution, we had 203 patients present with fractured neck of femur in 2018 and in the first 6 months of 2019 we have had 79. This is an average of 15.67 per month. Presuming this average continues and we achieve an enrolment rate of 80% and a PENG block delivered to one-third of these patients, we could expect to enrol sufficient patients in 6 months. To ensure significant power is achieved, we plan to enrol patients for a minimum of 6 and a maximum of 8 months.

Enrolment may be terminated early if we achieve a minimum enrolment of 125 patients and 41 PENG blocks. These numbers would allow for assessment of superiority (two-sided test) sensitive to a difference in pain score reduction of 1.3/10. [Appendix 3]

Secondary Outcomes

In an attempt to measure patient important outcomes, we will collect data on:

- Onset Time for analgesia (defined as the time until the first pain recorded pain score that is $\geq 1.5 / 10$ less than the pre-block pain score.
- Subjective observed patient comfort during nursing cares
- Patient preference where crossover occurs.
- Rates of block failure
- Block duration of analgesia

Subjective observed patient comfort during nursing cares:

Nursing staff caring for patients will be asked to comment on the patient's pain during standard nursing cares that require movement. These may include:

- Transfer to or from a bed
- Transfer on and off a bedpan
- Change of bedding or pad
- Other

At the time of nursing care, nurses are asked to rate the patient's analgesia as adequate or inadequate

Patient Preference where crossover occurs

- Some patients will have a repeat nerve block in the preoperative phase
- Of this population, some will receive a nerve block that is different to the block they received in ED. Hence they will have received cross over treatment and can act as their own control to compare two blocks.
- Investigators will identify these patients and they will be asked which block they found to provide more comfort.

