- ❑ Documentation on a paper form SPIED ED Data Form [Appendix 4] in the emergency department. This is additional to usual documentation and may be replaced by utilising Medical Surveys for data entry in the ED.
- ❑ Subjective Observed Patient Comfort During Nursing Score. May be completed in paper form [Appendix 7] or within Medical Surveys.

Data Governance

Data Storage:

The completed SPIED ED Data Form [Appendix 4] will be filed by clinicians in a folder within the Acute clinical area of the Emergency Department at Lismore Base Hospital. The SPIED ED Data Form will be the enrolment record.. Completed forms will be frequently collected by the investigators and stored securely with the ED Support Offices, which require swipe card access. This data will be stored for 5 years after the completion of data collection and then destroyed.

All other paper forms associated with the SPIED Study will form part of the patient's hospital record and will be treated accordingly.

Data Access:

- Investigators who are clinicians at Lismore Base Hospital have access to the patient's electronic medical records in the usual fashion as they would for day to day clinical work.
 - Investigators who access a patient's file for the purpose of data collection rather than clinical care, will create an electronic entry to document that they are accessing the file for the purposes of the SPIED study.
- In the event that any research funding is obtained, a research assistant may have access to Medical Surveys data and eMR as do the investigators.

Statistical Analysis

Primary Outcome:

Reduction in pain scores over the first 12 hours after nerve block. We will apply the following statistical tests:

- Student's t-test to compare the reduction in pain score of patients who receive a PENGGB compared to FNB and FICB
 - Subgroup analyses of the cognitively impaired and non-cognitively impaired population. These populations will have pain scored by the PAINAD and VAS respectively.
 - Subgroup analysis of FNB and FICB separately

Secondary Outcomes

- Onset of block. Defined as the time until the first pain score ≥ 1.5 less than the pre-block pain score.
 - T-test
- Subjective observed patient comfort during nursing cares
 - Chi Square test
- Patient Preference in the event of crossover
 - Chi Square test
- Rates of block failure. Defined as not achieving a reduction in pain score of $\geq 1.5 / 10$
 - Chi square test

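### The primary t-test has no defined value per patient: the protocol fixes no time, summary or condition (rest or movement), and the window closes at theatre, so most natural summaries depend partly on waiting time

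*Protocol*

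**What the plan says.** All references are to the Protocol.

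- The outcome section is headed "Primary outcome = reduction of pain score". It says "VAS pain scores will be recorded at rest and on movement", while for cognitively impaired patients "PAINAD scores will be single measure based on nursing observation".
- Scores are taken before the block, at "15, 30, 60 minutes post placement of block", and then "With routine limb observations on the surgical inpatient ward, approximately hourly". The limb-chart item under Additional Documentation gives the ward interval as one to two hours.
- The outcome section ends collection at 12 hours, or at the next score recorded after that, or when the patient goes to the operating room if sooner. The Surgery Waiting Time section ends primary-outcome collection at theatre check-in or 12 hours, with no allowance for a later score.
- Statistical Analysis, Primary Outcome, gives "Reduction in pain scores over the first 12 hours after nerve block" and then "Student's t-test to compare the reduction in pain score of patients who receive a PENGGB compared to FNB and FICB".
- The Minimum Sample Size Calculation rests on a "difference in pain score reduction of 1.5", SD 2.4, one-sided 0.05, power 0.80 and 1:2 allocation, giving 74 (25+49).
- Under Current Practice, the treating clinician decides which block is given.

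**The concern.** A two-sample t-test compares one number per patient. Here each patient supplies a series, in two conditions if scored by VAS, and nothing says how the series becomes one number. The section names the test and the 12-hour window, and the study is sized on one pain score reduction, so the gap lies in what the protocol itself fixes. For two secondary outcomes the protocol does make such choices: block failure uses the maximum improvement, and the analysis section's definition of duration uses pain on movement. The primary outcome has neither.

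The stopping rule adds a second difficulty. Follow-up length varies with theatre timing, so summaries taken over whatever window a patient happens to have are not like for like. Blocks are not randomised, so nothing in the design equalises waiting time between block groups. If waiting time differs, part of that difference would be read as a block effect. And if the time or condition were chosen after seeing results, the stated 5% error would no longer apply.

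**Working it through.** **1. The protocol's own sample size.** Inputs from the Minimum Sample Size Calculation: difference 1.5, SD 2.4, one-sided 0.05, power 0.80, ratio 1:2. Smaller group:

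n = (1 + 1/2) × (1.645 + 0.842)² × 2.4² / 1.5² = 1.5 × 6.18 × 2.56 ≈ 23.7, so 24, and 48 in the larger group (72 in all).

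By the noncentral t, power is 0.797 at 24+48 and 0.809 at 25+49. The stated 74 therefore reproduces.

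**2. Values available per patient.** Fixed early times: 3 (15, 30 and 60 minutes). Hourly ward times from 2 to 12 hours: 11. Total 3 + 11 = 14 post-block times, hence up to 28 VAS readings (rest and movement) or 14 PAINAD readings. With two-hourly ward scores (2, 4, ..., 12 hours) it is 3 + 6 = 9 times. These are upper limits, since theatre cuts them short.

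**3. Dependence on theatre time.** Assumed profile, not from the documents: true reduction 4 up to 6 hours, then 4 − 0.5 × (t − 6), reaching 1 at 12 hours. For the full window, the eight times to 6 hours sum to 32 and the six later ones to 3.5 + 3 + 2.5 + 2 + 1.5 + 1 = 13.5, so the mean is 45.5/14 = 3.25. The last column uses the same fade with an assumed gradual onset: 1 at 15 minutes and 2.5 at 30 minutes, which takes 3 + 1.5 = 4.5 off each sum.

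| Window ends | Times | Last value | Mean, immediate onset | Mean, gradual onset |
|---|---|---|---|---|
| 3 h | 5 | 4.0 | 20/5 = 4.0 | 15.5/5 = 3.1 |
| 6 h | 8 | 4.0 | 32/8 = 4.0 | 27.5/8 = 3.44 |
| 8 h | 10 | 3.0 | 38.5/10 = 3.85 | 34/10 = 3.4 |
| 12 h | 14 | 1.0 | 45.5/14 = 3.25 | 41/14 = 2.93 |

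One and the same block effect yields different patient values. Between 6 and 12 hours the last value moves by 3.0, twice the 1.5 used for sizing. The mean moves by 0.75 (half of it) with immediate onset and 0.51 with gradual onset. Between 3 and 12 hours with gradual onset, it moves by only 0.17.

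Suppose patients were of just two kinds, window ending at 6 or at 12 hours, and the block groups differed by a proportion d in the share followed to 12 hours. With no true block difference, the spurious difference would be 3.0 × d for the last value and 0.75 × d for the mean (immediate onset). The protocol gives nothing from which to estimate d.

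**4. The maximum depends on the number of scores.** Simulation of 200,000 patients, assuming a constant true reduction of 4, SD 2.4 for a single change, equal variances and one common correlation (0.3, 0.5 or 0.7, with nearly identical results): the maximum reduction averages 5.4 with 3 scores, 6.2 with 6 and 6.9 with 14. It rises with the number of scores alone.

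**5. The SD depends on the summary.** Under the same assumptions the SD of the mean of m reductions is 2.4 × √((1 + 1/m)/2). For m = 1 this is 2.4 (power 0.81 at 25+49); for m = 14 it is 2.4 × √(15/28) = 1.76 (power 0.96). The planned power thus cannot be attached to a summary until one is named.

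**The case against.** The strongest reply is that the protocol states one t-test of one reduction, and that a per-patient mean over 12 hours would be a legitimate single value with, on the assumptions above, ample power. That stands as far as it goes: a summary could be chosen and the test would run. But the protocol does not choose it, and the stopping rule would still make it depend on waiting time.

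Three stronger readings are tempting, and the document does not support them.

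- *A reader might infer that up to 28 separate tests are planned and that the error rate is inflated accordingly.* Simulating 14 two-sided tests at 25 v 49, with assumed correlations of 0.8 to 0.5, gives a 19–36% chance of at least one p<0.05 under no difference. But the protocol nowhere proposes testing time by time, it sizes the study on a one-sided non-inferiority test, and 14 and 28 are upper limits. These rates are hypothetical.
- *A reader might infer that the 5% error and 80% power belong to a single fixed-time comparison.* The sample-size section says only that a reduction differs by 1.5 with SD 2.4. It does not say at what time, or over what period.
- *A reader might infer that truncation at theatre biases the comparison.* No theatre-time distribution is given, and nothing shows that waiting time differs by block. If it does not, truncation changes what is being estimated and adds noise, but does not favour either block. The exposure is real because allocation does not balance waiting time; its size is unknown.

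It is also fair to say that moving the primary to 60 minutes is not a neutral repair. The stated interest is 12 hours, and the Comparison of Nerve Blocks section expects faster onset for PENG and prolonged onset for FICB.

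**Conclusion.** The point holds in this form: the primary outcome names a test and a window but no time, summary or condition, and the window closes at theatre. A last or maximum reduction, and to a lesser degree a mean, therefore depends partly on time to theatre in an unrandomised comparison. This conclusion rests on the text alone. The sizes in the working (last value 4.0 against 1.0; mean 4.0 against 3.25, narrower with gradual onset) rest on assumed profiles and show only that the effect can be large relative to 1.5. The sample-size arithmetic is not in error. The two statements of when the window ends also need reconciling. The matter should be settled before any comparison of the block groups.

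**What to change.** Before any comparison is made:

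1. Name one condition for the primary outcome, for example pain on movement for VAS patients with the single score for PAINAD patients. Make rest pain secondary. The subgroup analyses by scale, already planned, show whether pooling the two scales is reasonable.
2. Name one contrast that does not depend on when a patient goes to theatre, and replace the t-test on raw reductions with a baseline-adjusted model. Either of these would do:
   - a mixed model for repeated measures over scheduled times (block, time, block-by-time, baseline) with one prespecified contrast, such as an equally weighted average over named times. Ward scores need assigning to nominal times, and the assumption that leaving for theatre is unrelated to unseen pain, given the scores already seen, should be stated;
   - a baseline-adjusted linear model at one fixed time. The 60-minute score is one option, as the last score at a fixed time. Its downside is that it says nothing about later analgesia and may favour a block with faster onset.
3. Reconcile the outcome section and the Surgery Waiting Time section on whether the next score after 12 hours counts.

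No new data are needed. The cost is protocol wording, a little more analysis work, and giving up an unrestricted 12-hour reduction as the primary quantity.

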Provides anaesthesia to the lateral femoral cutaneous nerve, which innervates the site of skin incision for surgical repair (in lateral approaches only)	Anaesthesia of only some of the nerve branches of the femoral nerve that supply the anterior hip capsule. No blockade of AON [15]. Unlikely to provide blockade of the obturator nerve.
Very low risk for direct neural damage due to remote injection points.	Prolonged onset due to distant injection point and slow spread.

PERICAPSULAR NERVE GROUP BLOCK

A preliminary audit at Lismore Base Hospital performed in May 2019, results show a trend toward reduced pain and morphine requirements n=6. The difference was not statistically significant.

ADVANTAGES	DISADVANTAGES
Utilises bony sonographic anatomy, therefore less variations in performance is expected.	Deeper site of infiltration requires higher technical skills.
Target site contains nerves branches that innervate the anterior hip capsule with greater frequency than FNB or FICB. Only technique that blocks the AON [15, 23]. Closer proximity to obturator nerve branches than other techniques [15]. Makes obturator blockade very likely..	Sonographic anatomy not familiar to emergency physicians. Requires re-training and experience in ultrasound guided needle techniques.
Targets small, distal purely sensory nerves [15, 23]. This should convey a faster onset and more complete blockade. Rapid onset is particularly valuable in the emergency department, where the patient is likely to be moved soon after the block is inserted.	Not well established clinical practice. Quality evidence not yet produced.
Infiltration site is distant from major vasculature, so LAST is less likely. It is distant to any motor nerves which eliminates the risk for major motor nerve damage.	

Aims and Objectives

1. To confirm that the PENGGB is a safe and effective intervention for analgesia of patients presenting to the emergency department with hip fractures.
2. To perform a prospective observational study to assess the PENGGB comparing analgesic efficacy vs current practice of FICB and FNB

Null hypothesis

The PENGGB provides comparable analgesia to patients with fractured neck of femur compared to the FNB and FICB.

Study Design

A prospective observational study.

Current Practice:

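### Primary comparison: with an expected 1:2 split and no SD for PENG, Welch's t-test is a safer choice than Student's pooled-variance test (low-priority improvement)

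*Protocol*

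**What the plan says.** Under Statistical Analysis, Primary Outcome, the protocol specifies "Student's t-test to compare the reduction in pain score of patients who receive a PENGGB compared to FNB and FICB", with further analyses by cognitive status and against FNB and FICB separately.

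The section on sample size and statistical power rests on the same test: "Minimum Sample Size Calculation: Application of Student's t-Test". Its inputs include "One-sided test to assess for non-inferiority", "Sample allocation ratio of 1:2", "Standard Deviation = 2.4", a "difference in pain score reduction of 1.5" and "Target (Actual) Power = 0.8000", giving 74 patients (25+49). A second design, for two-sided superiority at a difference of 1.3, is reached at 125 patients with 41 PENG blocks (41+84).

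The 1:2 ratio is an expectation, not an assignment. Under Current Practice the treating clinician chooses the block, and Duration of Data Collection presumes that one-third of patients will receive PENG.

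On spread, the protocol cites SDs of 2.2 for FNB and 2.4 for FICB from an earlier trial. It has none for PENG: the local audit had six PENG patients, and its pain scores were judged too unreliable for power calculations. Unequal variances are not mentioned. The SAP is not at hand and may already deal with them.

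**The concern.** Student's t-test estimates one common variance, weighted towards the larger group. With equal groups this does little harm when the true variances differ. With a 1:2 split it does not balance out. If the smaller group (PENG) is more variable, the pooled standard error is too small and the test rejects too often. If PENG is less variable, the test rejects too rarely and loses power. In the first case the excess error makes a false finding of non-inferiority or superiority for PENG more likely, in a study whose results the investigators expect to influence uptake. Enrolling more patients in the same ratio does not remove the effect.

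**Working it through.** **1. The plan's own figures.** Normal approximation, smaller group, ratio 1:2: n = (z_alpha + z_power)² × SD² × (1 + 1/2) / difference².

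- Minimum design: (1.645 + 0.842)² × 2.4² × 1.5 / 1.5² = 23.7, so 24+48 = 72. With the noncentral t, power is 0.797 at 24+48 and 0.809 at 25+49. The stated 74 (25+49) is sound.
- Superiority design: (1.960 + 0.842)² × 2.4² × 1.5 / 1.3² = 40.1, so 41 PENG patients. Power by the noncentral t at 41+84 is 0.805. This is also sound.

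**2. Why the split matters.** Let PENG be group 1 (n1 = 25) and the comparators group 2 (n2 = 49).

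- Variance that Student's test uses: s_p² × (1/n1 + 1/n2), where s_p² = [(n1−1)s1² + (n2−1)s2²] / (n1+n2−2).
- True variance of the difference: s1²/n1 + s2²/n2.

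For assumed SDs of 3.0 and 2.4:

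- s_p² = (24 × 9.00 + 48 × 5.76)/72 = 6.84.
- Pooled variance of the difference = 6.84 × (1/25 + 1/49) = 0.413, so SE = 0.643.
- True variance = 9.00/25 + 5.76/49 = 0.478, so SE = 0.691.
- Ratio of SEs = 0.930. Approximate two-sided error = 2 × Φ(−1.96 × 0.930) = 6.8%. One-sided = Φ(−1.645 × 0.930) = 6.3%.

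**3. Simulated type I error of Student's test** (normal data, at least 400,000 runs per setting, nominal 5%). Only the values 2.2 and 2.4 come from the protocol, and both belong to comparator blocks. Assigning any SD to PENG is an assumption.

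| SD PENG / comparators | 25+49 one-sided | 25+49 two-sided | 41+84 two-sided |
|---|---|---|---|
| 2.4 / 2.4 | 5.0% | 5.0% | 5.0% |
| 2.2 / 2.4 | 4.5% | 4.4% | 4.4% |
| 2.4 / 2.2 | 5.5% | 5.7% | 5.7% |
| 3.0 / 2.4 | 6.3% | 6.8% | 6.9% |
| 3.6 / 2.4 | 7.4% | 8.4% | 8.7% |
| 2.4 / 3.0 | 3.9% | 3.6% | 3.5% |

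Welch's test stays between 4.9% and 5.1% in every row. With equal groups (37+37) Student's test also stays close to 5% (4.9% to 5.2%), so the unequal split is what makes the difference.

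**4. Power.**

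- Equal SDs of 2.4: at 25+49, one-sided, difference 1.5, Student 0.809 and Welch 0.806. At 41+84, two-sided, difference 1.3, Student 0.806 and Welch 0.802. The cost is 0.3 to 0.4 percentage points.
- PENG more variable, 25+49, one-sided: at 3.0/2.4, Student 0.73 and Welch 0.69. At 3.6/2.4, Student 0.66 and Welch 0.58. Part of Student's apparent advantage is its inflated error.
- Comparators more variable (2.4/3.0), 25+49, one-sided: Student 0.71 and Welch 0.74.

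**The case against.** The strongest reply is that no material difference in SD has been shown. The only block-specific SDs in the protocol are nearly equal, and a gap of that size between PENG and the comparators moves the error by less than one percentage point. The SDs of 3.0 and 3.6 are assumptions. This stands, and it sets the priority of the point.

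A reader might infer from the block comparison tables that PENG outcomes must vary more, since that block "Requires re-training and experience in ultrasound guided needle techniques". The documents do not support this. The remark concerns how the block is performed, not the SD of pain reduction, and the same table expects more uniform performance because the landmarks are bony. Nor does combining two comparator techniques widen the spread much. An equal mix of SDs 2.2 and 2.4 has SD √((4.84 + 5.76)/2) = 2.30. Even if the two block means differed by 1.5 points, it would be √(5.30 + 0.75²) = 2.42.

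A reader might also conclude that the primary test is invalid, or that its error is materially wrong whenever the SDs differ at all. That goes too far: the drift matters only from an SD ratio of about 1.25, and it depends on the split actually achieved.

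The separate FNB and FICB comparisons give little ground for concern. If the 49 comparators divide about evenly (an assumption), each is roughly 25 against 25, where Student's test holds 5.0% to 5.1% at 3.0/2.4 and 3.6/2.4.

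Finally, the variance form of a t-test is often settled in the SAP. Here, however, the protocol names Student's test in both the analysis and the sample-size sections, so a comment on that choice is fair.

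**Conclusion.** The point holds as a low-priority improvement. The protocol names a pooled-variance test for groups expected to be 1:2 in size and has no PENG SD to support pooling. If the SDs are as close as 2.2 and 2.4, nothing of consequence follows (4.4% to 5.7% two-sided). At assumed SD ratios of 1.25 to 1.5 with PENG the more variable, the two-sided error is about 6.8% to 8.4%. With the comparators more variable at 2.4/3.0, it is about 3.6%. These figures assume normal data and the expected split of 25+49, and they are nearly the same at 41+84.

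The sample size of 74 is correct and is not called into question. If PENG did prove more variable, power would fall below 0.80 under either test, because the planning SD of 2.4 would then be too small. That is a consequence of the variance itself, not of choosing Welch's test.

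**What to change.** In Statistical Analysis, Primary Outcome, name Welch's unequal-variance t-test for PENG against FNB and FICB combined. If an adjusted model is used, robust standard errors serve the same purpose. Use Welch's test in the separate FNB and FICB comparisons too, but only for consistency. Settle this before outcome data are seen, so that the form of the test is not chosen from the results. If the SAP already specifies it, align the protocol wording.

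The cost is a change of wording and 0.3 to 0.4 percentage points of power if the SDs are equal. No extra patients or data are needed to make the change. It does not address confounding by the clinician's choice of block, which is a separate matter.
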